4.1 Appendix 1: List of datalistings for each dose allocated report

4.1.1 Summary of patient treatment on cycle 1 (D1 – D21)

Datalisting 1. Demographic characteristics and treatment: Patient's center, number, age at inclusion, sex, Trabectedin start date, Trabectedin dose, Trabectedin perfusion interrupted, Trabectedin Relative Dose intensity, Durvalumab start date, Durvalumab dose, Durvalumab perfusion interrupted, Durvalumab Relative Dose intensity, C2D1 theoretical date, C2D1 real date.

4.1.2 Listing of adverse events for each patient cycle 1 and after

Datalisting 2. Adverse event: : Patient's center, number, date of event, Event number, DLT, serious adverse event, adverse event, initial intensity, maximum intensity, treatment modification, imputability, outcome, date of the end or death.

4.1.3 Listing of adverse events with any changes in grade

Datalisting 3. Adverse event with changes : Patient's center, number, date of event, serious adverse event, adverse event, initial intensity, maximum intensity, Date of change, New grade, outcome.

4.1.4 Listing of serious adverse events (SAE) for each patient

Datalisting 4. Serious adverse events: Patient's center, number, sae start date,, adverse event, serious adverse event, SOC, initial intensity, maximum intensity, treatment modification, imputability, outcome, date of the end or death.

4.2 Appendix 2: List of datalistings at the end of the escalation part and at the end of the expansion part

Each datalisting will be described according to the phase of the study (escalation part OR expansion part).

4.2.1 Inclusion form

Datalisting 1.1. Demographic characteristics: patient's number, center, birth date, histology, date of inclusion, sex, signed and dated written informed consent

Datalisting 1.2. Inclusion and non-inclusion criteria.

4.2.2 Tumor assessment: Baseline

Datalisting 2.1. Measurable lesions: Date of measurement, number of lesions, site, localisation description, measure, method, centralized review

Datalisting 2.2. Non-measurable lesions: Date of measurement, number of lesions, site, localisation description, evaluation, method, centralized review

4.2.3 Drug delivery

Datalisting 3.1. Durvalumab: start and end date, dose, therapy change, main reason for change, pills returned at pharmacy, total dose received during each cycle

Datalisting 3.2. Trabectedine: start and end date, dose, therapy change, main reason for change, pills returned at pharmacy, total dose received during each cycle

4.2.4 Tumor assessment

Datalisting 4. Tumor response: Date of measurement, Disease evaluation, sum of the largest diameters, new lesions, target lesions, non-target lesions, overall response, treatment continuation, centralized review

4.2.5 End of treatment

Datalisting 5. End of treatment: start and end dates of treatment, status (complete response,...), reason for the end of the treatment, date of progression, type of progression

4.2.6 Adverse event

Datalisting 6.1. Adverse event: Event number, adverse event, serious adverse event, sae start date, soc, date of event, initial intensity, maximum intensity, treatment modification, imputability, outcome, date of the end or death

Datalisting 6.2. Serious adverse events: SAE number, adverse event, serious adverse event, sae start date, soc, date of event, initial intensity, maximum intensity, treatment modification, imputability, outcome, date of the end or death

4.3 Appendix 2 : List of Tables and Figures

4.3.1 Study populations

Table 1.1. Description of center

Table 1.2. First and last consent date, date of last end study.

Table 1.3. Number of patients registered, treated, eligible, eligible and assessable for efficacy, assessable for safety

4.3.2 Patient characteristics at baseline

Table 2. Demographic characteristics and general medical conditions at baseline for each study populations: age, sex, weight, height, Heart rate, blood pressure, body temperature, performance status

4.3.3 Tumor characteristics at baseline

Table 3. For each study population: description of disease diagnosis, histological diagnosis, anatomic location, grade, type of event (initial / relapse), metastasis (Y/N), sites of Metastasis and prior treatment (surgery, radiotherapy, chemotherapy)

4.3.4 Drug delivery

Table 4.1. For all patients registered: Frequency of delivered cycle of Durvalumab.

Table 4.2. For all patients registered: Frequency of delivered cycle of Trabectedine.

Table 4.3. For each study population: number of reduction, delay and discontinuation (temporary stop and definitive stop) and reasons

4.3.5 End of treatment

Table 5.1. For each patient registered: Dates of start and end of treatment, number of cycle received, status at end of treatment, reason for end of treatment

Table 5.2. For each patient eligible: Dates of start and end of treatment, number of cycle received, status at end of treatment, reason for end of treatment

Table 5.3. For each patient eligible and assessable for efficacy: Dates of start and end of treatment,

number of cycle received, status at end of treatment, reason for end of treatment

Table 5.4. For each patient assessable for safety: Dates of start and end of treatment, number of cycle received, status at end of treatment, reason for end of treatment

4.3.6 Objective response

Table 6.1. For each patient eligible and assessable for efficacy: Dates of start and end of treatment, date, new lesions and response at each tumor evaluation (week 6, week 12, week 18, week 24 and end of treatment), status at the end of treatment, date and type of progression

Table 6.2. For all patients eligible and assessable for efficacy: Frequency and rate with 95% confidence interval (binomial law) of objective responses observed at the 6-month evaluation

Table 6.3. For each arm of treatment: Frequency and rate with 95% confidence interval (binomial law) of each category observed as objective response

Table 6.4. For all patients eligible and assessable for efficacy: Frequency and rate with 95% confidence interval (binomial law) of objective responses observed during the first 6 months (whatever the evaluation time)

Table 6.5. For each arm of treatment: Frequency and rate with 95% confidence interval (binomial law) of each category observed as objective response (whatever the evaluation time)

4.3.7 Best response

Table 7.1. For all patients eligible and assessable for efficacy: Frequency and rate with 95% confidence interval (binomial law) of each category observed as best response

Table 7.2. For each arm of treatment: Frequency and rate with 95% confidence interval (binomial law) of each category observed as best response

4.3.8 6-month non-progression

Table 8.1. For each patient eligible and assessable for efficacy: Dates of start and end of treatment, date, new lesions and response at each tumor evaluation (week 6, week 12, week 18, week 24 and end of treatment), status at the end of treatment, date and type of progression

Table 8.2. For all patients eligible and assessable for efficacy: Frequency and rate with 95% confidence interval (binomial law) of non-progression observed at the 6-month evaluation

Table 8.3. For each arm of treatment : Frequency and rate with 95% confidence interval (binomial law) of non-projection observed at the 6-month evaluation

Table 8.4. For all patients eligible and assessable for efficacy: Frequency and rate with 95% confidence interval (binomial law) of non-projection observed during the first 6 months (whatever the evaluation time)

Table 8.5. For each arm of treatment : Frequency and rate with 95% confidence interval (binomial law) of non-projection observed during the first 6 months (whatever the evaluation time)

4.3.9 Progression-free survival

Table 9.1. For all patients eligible and assessable for efficacy: Median PFS, 6-month PFS rate and 1-year PFS rate

Table 9.2. For each arm of treatment: Median PFS, 6-month PFS rate and 1-year PFS rate

Figure 1: Kaplan-Meier – PFS curves – Patients eligible and assessable for efficacy

4.3.10 Overall survival

Table 10.1 For all patients eligible and assessable for efficacy: Median OS, 6-month OS rate and 1-year OS rate

Table 10.2. For each arm of treatment: Median OS, 6-month OS rate and 1-year OS rate

Figure 2: Kaplan-Meier – OS curves – Patients eligible and assessable for efficacy

4.3.11 Safety: Adverse events (AE)

Table 11.1. For all patients assessable for efficacy: Number and percentage of AE observed by SOC and type of event

Table 11.2. For each patient assessable for safety: Event number, adverse event, serious adverse event (Y/N), SOC, date of event, initial intensity, maximum intensity, treatment modification, imputability, outcome, date of the end or death

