4.8. EVALUATION AT the END OF TREATMENT

The end-of-treatment visit will be scheduled 30 days (4 weeks) after the last treatment administration (a window of ± 1 week is allowed).

Regardless of the reason for discontinuation, the complete workup has to be done at the end-of-treatment visit. This will include the following assessments:

- Assessment of signs and symptoms.
- Complete physical examination.
- ECOG performance status.
- Vital signs [heart rate, blood pressure, weight and temperature].
- Hematology.
- Biochemistry.
- Urinalysis
- Calculated CrCl.
- Thyroid function

- CA 125 measurement
- Clinical and radiological tumor assessment (CT-scan/MRI) (except for patients with confirmed PD at discontinuation or who had started a new treatment).
- Intercurrent events and concomitant disease and treatments.
- Safety assessment (AEs).

Adverse events must be reported for 30 days after the last treatment administration or until the start of a new antitumor therapy, whichever occurs first. All SAEs occurring within 90 days of the last treatment administration or until the start of a new antitumor therapy, whichever occurs first, will be reported. Beyond this period of time, only those SAEs suspected to be treatment-related will be reported (see Section 11).

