9.2.2. Phase I (Expansion cohorts)

- Eligible population: All patients included without major violation of eligibility criteria.

- Population assessable for efficacy: All patients eligible and for whom the following conditions are satisfied:
 - Received at least one complete or two incomplete treatment cycles,
 - At least one disease measurement recorded not less than six weeks after treatment onset.
- The following patients will also be included in the population assessable for efficacy; they will be considered as "inevaluable for response" for the primary endpoint as per RECIST v1.1 criteria (i.e. objective response under treatment) and not be replaced in the primary efficacy analysis:
 - Any eligible patients who received at least one treatment cycle or two incomplete treatment cycles and experience disease progression or die due to disease progression prior to response evaluation (will be considered as "inevaluable for response" due to early progression).
 - Patients withdrawn due to drug-related toxicity without any tumor assessments after the start of study treatment (will be considered as "inevaluable for response" due to toxicity).
 - Patients who received at least one administration of the treatment AND withdrawn due to significant clinical deterioration of unknown reason AND without any tumor assessments after the start of study treatment (will be considered as "inevaluable for response" due to significant clinical deterioration).
- Safety population: all patients having received at least one (any) treatment administration.

Patient's replacement:

- Any patient not eligible or not assessable for efficacy will be replaced.
- However, any patient who received at least one administration of the study drug will be included in the safety analysis.

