3.2.2 Expansion cohorts

- Analyses will be conducted separately for sarcoma and ovarian cancer patients.
- Primary efficacy endpoint will be analysed based on the eligible and assessable population:
 - Each patient will be assigned one of the following categories:
 - Complete response
 - Partial response
 - Stable disease
 - Progression
 - Inevaluable for response
 - The rate of objective response (complete or partial response) under treatment will be reported:
 - All eligible and assessable patients will be included in the denominator for the calculation of the objective response rate (ORR).
 - The 95% two-sided confidence limits will be provided for the ORR (binomial law).
 - First endpoint conclusions will be based on the objective response rate ORR for all eligible and assessable patients (section 10.2) after centralized radiological review of the data.
- As regards to the other efficacy endpoints, the analyses will be carried out in the eligible and assessable population:
 - Each patient will be assigned one of the following categories:
 - Complete response
 - Partial response
 - Stable disease
 - Progression
 - Inevaluable for response
 - The rate of best overall response will be calculated as the number of patients alive with the best response (recorded from the start of the treatment) divided by the number of patients eligible and assessable.
 - The 6-month progression-free rate will be calculated as the number of patients remaining alive and progression-free at 6 months from the start of the treatment divided by the number of patients eligible and assessable.
 - The 6-month objective response rate will be calculated as the number of patients alive with complete or partial response at 6 months divided by the number of patients eligible and assessable.
 - The 95% two-sided confidence limits will be provided for the calculated rates (binomial law)
- The safety analysis will be performed on the safety population.
- Quantitative variables will be described using mean and standard deviations if the normality assumption is satisfied, else other descriptive statistics (median, range, quartiles) will be reported.
- Qualitative variables will be described using frequency, percentage and 95% confidence interval (binomial law).
- Survival endpoints will be analysed using the Kaplan-Meier method. The median survival rates will be reported with a 95% confidence interval. Median follow-up will be calculated using the reverse Kaplan-Meier method.

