4.3.12 Safety: Serious adverse events (SAE)

Table 12.1. For all patients assessable for efficacy: Number and percentage of SAE observed by SOC and type of event

Table 12.2. For each patient assessable for safety: Event number, adverse event, SOC, date of event, initial intensity, maximum intensity, treatment modification, imputability, outcome, date of the end or death

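### SAP Tables 11.1 and 12.1 count adverse events on the efficacy-assessable patients instead of all treated patients, and escalation toxicity is restricted to the DLT-evaluable set

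*SAP*

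**What the plan says.** **Expansion cohorts.** The two frequency tables are specified as "Table 11.1. For all patients assessable for efficacy: Number and percentage of AE observed by SOC and type of event" (SAP 4.3.11) and "Table 12.1. For all patients assessable for efficacy: Number and percentage of SAE observed by SOC and type of event" (SAP 4.3.12). The methods text in SAP 3.2.2 reads "The safety analysis will be performed on the safety population". SAP 2.1.2 and 2.4 define that population as all patients with at least one administration, and SAP 2.4 codes it as SAF=1. Protocol 9.2.2 covers replaced patients explicitly: "any patient who received at least one administration of the study drug will be included in the safety analysis". Protocol 7.3, 9.3.2.2 and Appendix 3 agree.

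**Dose escalation.** Protocol 8.1 makes graded toxicity part of the primary endpoint, next to DLT incidence. Protocol 9.3.2.1 analyses that endpoint on the population assessable for safety. SAP 3.2.3 implements this with the filter TOL=1 over both the toxicity row and the DLT row. Protocol 9.2.1 and SAP 2.3 remove two kinds of dosed patient from that set: those at or below 75% relative dose intensity (RDI) in cycle 1 because of a drug-related event not counted as a DLT, and those who left treatment in cycle 1 for reasons unrelated to toxicity. Protocol 7.3 and Appendix 3 count every treated patient as evaluable for toxicity.

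**The concern.** An adverse event frequency table should be run on everyone exposed. Here the tables that give numbers and percentages are tied to a set built for the response endpoint. Entry to that set depends on eligibility, cycles received and the timing of a scan.

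The escalation restriction has a different source. It is a tension within the protocol, which the SAP follows faithfully. A DLT-evaluable set is normal for the DLT rate. Applied to all graded toxicity, it makes inclusion depend partly on toxicity itself, because one exclusion reason is a drug-related event.

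The safety profile belongs to the primary objective, and protocol 3.4 uses data from all patients to define the RP2D. A treated patient missing from the summary tables is therefore missing from the main display of that evidence.

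**Working it through.** **1. The plan's own count.** Inputs from protocol 9.1.1 (expansion): 20% efficacy rate, 5% error, 14 assessable and 15 recruited per cohort. The Gehan first stage is the smallest n with (1 − 0.20)^n ≤ 0.05. Since 0.8^13 = 0.0550 and 0.8^14 = 0.0440, n = 14, as stated. The planned gap between recruited and assessable is 15 − 14 = 1 per cohort, or 2 of 30.

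**2. Who is treated but outside the efficacy set?** The main route into the set needs enough treatment and "At least one disease measurement recorded not less than six weeks after treatment onset". Exceptions keep some patients without that scan. Two examples of treated patients who can still fall out:

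- (a) A patient who leaves before week 6 without a scan, for an event judged unrelated to treatment.
- (b) A patient withdrawn for drug-related toxicity after cycle 1 whose only post-baseline scan is the end-of-treatment one. The toxicity exception covers "Patients withdrawn due to drug-related toxicity without any tumor assessments after the start of study treatment". But protocol 4.8 says "Regardless of the reason for discontinuation, the complete workup has to be done at the end-of-treatment visit", and the work-up includes imaging unless progression is already confirmed or a new treatment has begun. On timing, "The end-of-treatment visit will be scheduled 30 days (4 weeks) after the last treatment administration", with a window of ±1 week.
  - Last administration: day 1 or 2.
  - Earliest scan: 1 + 28 − 7 = day 22. Latest scan: 2 + 30 + 7 = day 39.
  - Six weeks after onset: 1 + 42 = day 43.
  - The scan is too early for the main condition, yet its existence defeats the exception. SAP Table 6.1 counts end of treatment as a tumour evaluation.

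The SAP 2.4 code for the toxicity branch joins AND and OR without grouping, so it does not settle case (b). An ineligible treated patient is outside the set by the text of SAP 2.4, but not by its ELI_EFF code, which has no eligibility condition. ELI_EFF is also defined only for the expansion cohorts, so Tables 11.1 and 12.1 have no defined population for escalation patients.

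**3. Size, expansion.** Assumption: the non-assessable patient was dosed. Event counts are also assumed. Intervals are Clopper-Pearson 95%.

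- Omitted: 1/15 = 6.7% per cohort. With replacement it can be more, for example 2/16 = 12.5%.
- SAE only in the omitted patient, as in case (b): 0/14 = 0.0% (0.0 to 23.2) shown, against 1/15 = 6.7% (0.2 to 31.9).
- Common event: 7/14 = 50.0% (23.0 to 77.0) shown, against 7/15 = 46.7% (21.3 to 73.4) if the omitted patient had no event, or 8/15 = 53.3% (26.6 to 78.7) if the patient did.

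**4. Size, escalation.** Assumption: one dose level with 6 patients at TOL=1 and 1 removed by the RDI rule. That patient had a drug-related event by definition. With 3 of the 6 affected, any drug-related event reads 3/6 = 50.0% (11.8 to 88.2) instead of 4/7 = 57.1% (18.4 to 90.1). The DLT rate is not lowered by TOL: 1/6 = 16.7%, against 1/7 = 14.3% on all treated.

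**5. Labels.** SAP 2.3 uses assessable for safety for TOL, and SAP 2.4 uses it in the value text for SAF. The SAF code sits under a heading that names the variable ELI_DLT. Tables 11.2 and 12.2 do not say which flag they use. SAP 2.3 excludes low-RDI patients but includes all who completed the DLT period, so a low-RDI completer fits both rules.

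**The case against.** The strongest reply is that this is a wording slip. Every governing text agrees on the rule, SAF is already coded, Tables 11.2 and 12.2 use a safety label, the listings hold all events, and no decision rule reads Tables 11.1 or 12.1. A slip is likely, but it occurs twice, and these lines specify the outputs to be programmed.

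The examples are also narrower than they may look. Points that stand:

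- Patients who stop without progression are followed every 12 weeks, so a later scan may bring case (b) back in.
- Early progression has its own exception.
- The code tests for a week 6 assessment, not a day 43 cut. With the ±7-day scan window (days 36 to 50), a scan on days 36 to 39 might be recorded as week 6.
- An unrelated event in case (a) might be coded as clinical deterioration and retained.

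These points make the cases conditional. They do not put all treated patients into the tables.

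On escalation, protocol 9.3.2.1 already asks for toxicity tables by dose level and cycle and for combined analyses where appropriate, so an all-treated summary is not forbidden. But that text does not lift the TOL=1 filter in SAP 3.2.3. It is fair that the 3/6 against 4/7 example depends on the unresolved status of low-RDI completers, and that the RDI code also requires an interrupted infusion.

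**Conclusion.** The point holds. SAP Tables 11.1 and 12.1 contradict the SAP's own methods text and the protocol, and as written they omit treated patients who are not assessable for efficacy. The number is small: 1 of 15 per cohort on the planned counts if that patient was dosed, 0 if not, and more if several are replaced. The direction is open in general. It is downward for an event that led to the omission, as in case (b), provided no later scan is recorded. The escalation restriction also holds, as an inconsistency inside the protocol that selects partly on toxicity. DLT incidence and the MTD rule are unaffected. All event counts above are illustrative. This should be corrected before the tables are produced.

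**What to change.** - Specify Tables 11.1 and 12.1 on the safety population (SAF=1), by study part, dose level and cohort.
- Keep TOL=1 for the DLT rate and MTD only. Summarise escalation graded toxicity by dose level on all treated patients, and amend protocol 9.3.2.1 and SAP 3.2.1 and 3.2.3 to say so.
- Clarify the flags: relabel TOL as DLT-evaluable, correct the ELI_DLT heading over the SAF code, and name the flag used in Tables 11.2 and 12.2.
- State whether a patient at or below 75% RDI who completes day 21 has TOL=1 or TOL=0.

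The cost is a header and filter correction in the SAP and one wording amendment in the protocol, with no new data. The protocol change may need ethics committee and authority approval under protocol 12.1. If that is impractical, an additional all-treated toxicity table in the SAP would supply the same information. Reported percentages may move slightly in either direction.

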4.3.12 Safety: Serious adverse events (SAE)

Table 12.1. For all patients assessable for efficacy: Number and percentage of SAE observed by SOC and type of event

Table 12.2. For each patient assessable for safety: Event number, adverse event, SOC, date of event, initial intensity, maximum intensity, treatment modification, imputability, outcome, date of the end or death
